7. STUDY ASSESSMENTS AND EVALUATIONS

7.1 Overview

All patients should visit the study center on the days specified within this protocol. The complete Schedules of Assessments for the two cohorts in this study are shown in Appendix A **Error! Reference source not found.** and Appendix B **Error! Reference source not found..**

Informed consent must be obtained ≤ 28 days prior to initiation of treatment and before any protocol-specific procedures are performed. The Screening physical examination, medical history, ECOG PS, complete blood counts (CBC), differential and platelets, comprehensive metabolic profile (CMP), and prothrombin time/partial thromboplastin time/international normalized ratio (PT/PTT/INR) should be done ≤ 21 days prior to initiation of treatment. A pregnancy test must be performed within 72 hours of Cycle 1 Day 1. CT scan of the chest, abdomen, and pelvis should be performed ≤ 28 days prior to initiation of treatment, as should a carcinoembryonic antigen (CEA) tumor marker.

Cohort 1 and Cohort 2 patients will be assessed to determine suitability for SIR-Spheres. These assessment tests will be obtained 7-4 days prior to SIR-Spheres treatment. Cohort 1 patients will have these assessments performed during week 4 prior to SIR-spheres treatment. Cohort 2 patients will be assessed at Screening.

Patients need to fast for 6 hours before receiving SIR-Spheres treatment.

Imaging studies to be submitted for central review are listed in Section 13.3.

7.2 Patient Assessment for SIR-Spheres

Cohort 1 and Cohort 2 patients will be assessed to determine suitability for SIR-Spheres.

The following tests will be obtained 7-4 days prior to SIR-Spheres treatment.

- **Hepatic angiogram**
- **99m Tc MAA lung shunt scan**

Cohort 1 patients will have these assessments performed during week 4 prior to SIR-spheres treatment.

Cohort 2 patients will be assessed at Screening 7-4 days prior to SIR-Spheres treatment on CID1.

7.3 Study Treatment Assessments - COHORT 1

7.3.1 Baseline Study Assessments

The following information will be collected and procedures will be performed for each patient at Screening ≤ 21 days prior to initiation of treatment unless otherwise noted:

- Written informed consent prior to any other study-related procedures (≤ 28 days prior to initiation of treatment)
- Medical history

CONFIDENTIAL

STUDY DEVICE: SIR-Spheres®

SCRI INNOVATIONS STUDY NUMBER: GI 189

DATE OF ORIGINAL PROTOCOL: 16 December 2013

Date of Amendment #1: 15 April 2014

Version 2.0

- Physical examination, measurements of height (first visit), weight, and vital signs (resting heart rate, respiratory rate, and oral temperature)
- Blood pressure (BP)
- ECOG PS (Appendix D)
- Concomitant medication review
- CBC (complete blood count) including hemoglobin, hematocrit, white blood cell (WBC) with 3-part differential, and platelets
- CMP to include: glucose, blood urea nitrogen (BUN), creatinine, sodium, potassium, chloride, calcium, carbon dioxide (CO₂), alkaline phosphatase (ALP), AST, ALT, total bilirubin, total protein, and albumin plus lactate dehydrogenase (LDH), and phosphorus.
- PT/PTT/INR
- Serum or urine pregnancy test (must be performed within 72 hours prior to the initiation of treatment)
- Disease assessments:
 - CT scan chest, abdomen, and pelvis (\leq 28 days prior to treatment)
 - CEA tumor marker

7.3.2 Cycle 1, Day 1

If the following are performed within 72 hours of Cycle 1 Day 1 they do not have to be repeated:

- Medical history
- Physical examination, measurements of weight, and vital signs (resting heart rate, respiratory rate, and oral temperature)
- BP
- ECOG PS
- Concomitant medication review
- CBC
- CMP
- PT/PTT/INR
- Serum or urine pregnancy test (must be performed within 72 hours prior to the initiation of treatment)
- CEA tumor marker

CONFIDENTIAL

STUDY DEVICE: SIR-Spheres®

SCRI INNOVATIONS STUDY NUMBER: GI 189

DATE OF ORIGINAL PROTOCOL: 16 December 2013

Date of Amendment #1: 15 April 2014

Version 2.0

7.3.3 Cycle 1, Day 8 and 15

- Physical examination, weight, and vital signs
- BP
- ECOG PS
- AE assessment
- Concomitant medication review
- CBC
- CMP
- PT/PTT/INR (for patients receiving Coumadin therapy)

7.3.4 Cycle 1, Day 22 (assessments to be completed \leq 7 days prior to SIR-Spheres treatment)

- Physical examination, weight, and vital signs
- BP
- ECOG PS
- AE assessment
- Concomitant medication review
- CBC
- CMP
- PT/PTT/INR (for patients receiving Coumadin therapy)
- Biomarker blood sample collection prior to the hepatic angiogram and 99m Tc MAA lung shunt scan
- CEA tumor marker

The following tests will be obtained 7-4 days prior to SIR-Spheres treatment:

- Hepatic angiogram
- 99m Tc MAA lung shunt scan

7.3.5 Cycle 2, Day 1

SIR-Spheres may not be administered until the patient's hematologic, liver and renal function assessments performed per Section 7.3.4 have been re-confirmed as eligible according to Section 3.1 by the Investigator.

- SIR-Spheres treatment
- BP

CONFIDENTIAL

STUDY DEVICE: SIR-Spheres®

SCRI INNOVATIONS STUDY NUMBER: GI 189

DATE OF ORIGINAL PROTOCOL: 16 December 2013

Date of Amendment #1: 15 April 2014

Version 2.0

7.3.6 Cycle 2, Day 8

- BP
- AE assessment
- CMP
- Biomarker blood sample collection (following SIR-Spheres treatment)

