3. STUDY PATIENT POPULATION AND DISCONTINUATION

3.1 Inclusion Criteria

Patients must meet the following criteria in order to be included in the research study:

1. Histologically confirmed metastatic adenocarcinoma of the colon or rectum.
2. Patients who have been previously treated with or are not candidates for fluorouracil, oxaliplatin, irinotecan, and if Kras wild-type, anti EGFR therapy
3. Considered an appropriate candidate for regorafenib therapy.
4. Measurable disease as measured by Response Evaluation Criteria in Solid Tumors (RECIST) version 1.1 (Appendix C).
5. Measurable computed tomography (CT) scan evidence of liver metastases which are not treatable by surgical resection or local ablation with curative intent at the time of study entry.
6. Eastern Cooperative Oncology Group (ECOG) Performance Status (PS) score of 0-1 (Appendix D).
7. Adequate hematologic function defined as:
 - Absolute neutrophil count (ANC) $\geq 1500/\mu\text{L}$
 - Hemoglobin (Hgb) $\geq 9 \text{ g/dL}$ (pre-enrollment transfusion allowed)
 - Platelets $\geq 75,000/\mu\text{L}$
8. Adequate liver function defined as:
 - Alanine aminotransferase (ALT) and aspartate aminotransferase (AST) $\leq 2.5 \times$ the upper limit of normal (ULN) or $<5 \times$ ULN if due to hepatic metastases
 - Total bilirubin $\leq 1.5 \times$ ULN (unless the patient has Grade 1 bilirubin elevation due to Gilbert's disease or a similar syndrome involving slow conjugation of bilirubin)
9. Adequate renal function defined as serum creatinine $\leq 1.5 \text{ mg/dL}$ (133 $\mu\text{mol/L}$) OR calculated creatinine clearance $\geq 50 \text{ mL/min}$.
10. Male patients with female partners of childbearing potential and female patients of childbearing potential are required to use two forms of acceptable contraception, including one barrier method, during their participation in the study and for 30 days following last dose. Male patients must also refrain from donating sperm during their participation in the study (Appendix E).
11. Life expectancy ≥ 3 months.
12. Age ≥ 18 years.
13. Ability to understand the nature of this study and give written informed consent.

CONFIDENTIAL

STUDY DEVICE: SIR-Spheres®

SCRI INNOVATIONS STUDY NUMBER: GI 189

DATE OF ORIGINAL PROTOCOL: 16 December 2013

Date of Amendment #1: 15 April 2014

Version 2.0

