3.2 Exclusion Criteria

Patients who meet any of the following criteria will be excluded from study entry:

1. Most recent chemotherapy \leq 14 days and \geq Grade 1 chemotherapy-related side effects, with the exception of alopecia.
2. Use of a study drug \leq 21 days or 5 half-lives (whichever is shorter) prior to initiation of study treatment. For study drugs for which 5 half-lives is \leq 21 days, a minimum of 10 days between termination of the study drug and administration of study treatment is required.
3. Wide field radiotherapy (including therapeutic radioisotopes such as strontium 89) administered \leq 28 days or limited field radiation for palliation \leq 7 days prior to starting study drug or has not recovered from side effects of such therapy.
4. Previous radiation delivered to the upper abdomen.
5. Major surgical procedures \leq 28 days of beginning study drug, or minor surgical procedures \leq 7 days. No waiting required following port-a-cath placement.
6. Previously untreated brain metastases. Patients who have received radiation or surgery for brain metastases are eligible if therapy was completed at least 2 weeks previously and there is no evidence of central nervous system disease progression, mild neurologic symptoms, and no requirement for chronic corticosteroid therapy.
7. Leptomeningeal metastases or spinal cord compression due to disease.
8. Pregnant or lactating.
9. Evidence of ascites, cirrhosis, portal hypertension, or thrombosis as determined by clinical or radiologic assessment.
10. History of abdominal fistula or gastrointestinal perforation \leq 6 months prior to beginning study treatment.
11. Serious non-healing wound, active ulcer, or untreated bone fracture.
12. Presence of active gastrointestinal disease or other condition that will interfere significantly with the absorption, distribution, metabolism, or excretion of oral therapy (e.g. ulcerative disease, uncontrolled nausea, vomiting, diarrhea Grade \geq 2, and malabsorption syndrome).
13. Any of the following cardiac diseases currently or within the last 6 months:
 - Unstable angina pectoris
 - Congestive heart failure (NYHA \geq Grade 2 [Appendix F])
 - Conduction abnormality not controlled with pacemaker or medication
 - Significant ventricular or supraventricular arrhythmias (patients with chronic rate-controlled atrial fibrillation in the absence of other cardiac abnormalities are eligible)

CONFIDENTIAL

STUDY DEVICE: SIR-Spheres®

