8. DRUG FORMULATION, AVAILABILITY, ADMINISTRATION, AND TOXICITY INFORMATION

8.1 SIR-Spheres[®] Microspheres

SIR-Spheres microspheres are to be administered in accordance with the terms of its marketing authorization and in accordance with institutional standard of practice. Please refer to the US Package Insert <http://www.sirtex.com/us/clinicians/package-insert> for detailed information on how to prepare and administer SIR-Spheres microspheres.

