8.1.2 Preparation and Administration of SIR-Spheres® Microspheres

SIR-Spheres microspheres should be prepared and administered in accordance with the terms of its marketing authorization. .

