Appendix A: Cohort 1 Schedule of Assessments (continued)

- a. Informed Consent must be obtained ≤ 28 days prior to the initiation of study treatment.
- b. The Screening physical examination, update of medical history, ECOG performance status, CBC, CMP, and PT/PTT/INR, and concomitant medication review should be done ≤ 21 days prior to initiation of treatment. However, if these initial examinations are obtained within 72 hours of Cycle 1 Day 1 they do not have to be repeated on Cycle 1 Day 1. Scans to document measurable or evaluable disease (i.e., tumor measurement) and tumor marker (CEA) should be performed ≤ 28 days prior to initiation of treatment.
- c. Physical examinations will include measurements of height (Screening visit only), weight and vital signs (resting heart rate, respiratory rate, oral temperature). Blood pressure should be monitored weekly for the first 6 weeks of regorafenib treatment and then every cycle, or more frequently, if clinically indicated.
- d. Hematology parameters include the following laboratory tests: complete blood count including WBC with 3-part differential (total neutrophil count including bands, lymphocytes, monocytes) hemoglobin, hematocrit and platelets.
- e. CMP must include glucose, BUN, creatinine, sodium, potassium, chloride, calcium, CO₂, ALP, AST, ALT, total bilirubin, total protein, and albumin plus LDH, phosphorus.
- f. If liver function toxicities are present after a 2 week rest, then patients may be rechecked weekly for 2 additional weeks. Reinitiation of regorafenib must be delayed until appropriate resolution of liver function toxicities.
- g. PT/PTT/INR will be monitored in patients receiving Coumadin on Days 1, 8 (Cycle 1 only) and 15 of each treatment cycle.
- h. Biomarker samples (see Section 5.4) will be collected from all patients prior to the hepatic angiogram and ^{99m}Tc MAA lung shunt scan, which will be obtained 7-4 days prior to SIR-Spheres treatment (see Section 7.2) and on Day 8 after SIR-Spheres treatment and Day 30 (pre-dose) after SIR-Spheres treatment.
- i. Serum or urine pregnancy tests are to be conducted in women of childbearing potential within 72 hours of C1D1.

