- j. CT scan of the chest, abdomen and pelvis will be obtained at baseline ≤ 28 days prior to the initiation of treatment. Assessments required the same day of SIR-Spheres administration can be obtained ≤ 7 days prior to SIR-Spheres treatment. Patients will be restaged on Week 6 and Week 12 after SIR-Spheres treatment according to RECIST v1.1. All assessments should be performed within 7 days of the schedule day of assessment. Patients with stable disease or better may continue treatment with regorafenib. CEA tumor markers must be assessed on Day 1 of each cycle and at the End of Treatment visit.
- k. Patients determined to have stable disease or better at the Week 12 restaging continuing treatment will begin 28-day treatment cycles (21 days oral regorafenib followed by one week rest). Patients will then be re-assessed according to RECIST v1.1 criteria every 8 weeks.
- l. All patients will undergo the End of Treatment visit assessments listed within 30 days after treatment ends due to completion of the planned study treatment period, or once a patient is discontinued due to unacceptable toxicity or decision to discontinue treatment by the patient or the study physician. If treatment is discontinued because of toxicity or any other reason(s) at a treatment visit and no study treatment is administered, that visit may fulfill the End of Treatment visit. After withdrawal from or completion of protocol treatment, patients must be followed for adverse events for 30 calendar days after the last dose of study drug.
- m. Patients will be followed every 3 months (± 1 month) for up to a maximum of 6 months after the last patient has enrolled on study for toxicity and disease progression.
- n. After disease progression is documented, patients will be followed every 3 months (± 1 month) for survival (e.g., date and cause of death) for up to a maximum of 6 months after the last patient has enrolled on study or death whichever comes first. Patients may be contacted during outpatient visits or by telephone.
- o. Patients will be assessed 7-4 days prior to SIR-Spheres treatment to determine the suitability for SIR-Spheres (see Section 7.2).
- p. Patients will self-administer regorafenib during Days 1-21.
- q. The Cycle 1 Day 22 physical examination, ECOG performance status, CBC, CMP, and PT/PTT/INR, tumor marker (CEA), adverse event evaluation, and concomitant medication review to be completed ≤ 7 days prior to SIR-Spheres radiation treatment.

STUDY DEVICE: SIR-Spheres®

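### Cohort 1 schedules no pregnancy test after regorafenib starts, so the only listed test is 28 to 31 days old at an on-schedule SIR-Spheres implant

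*Protocol*

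**What the plan says.** **The test.** Section 7.1 states the rule for both cohorts: "A pregnancy test must be performed within 72 hours of Cycle 1 Day 1". Sections 7.3.1 and 7.3.2 place the Cohort 1 test before treatment starts, and a test done inside that window need not be repeated on the day. Appendix A footnote i says the same: "Serum or urine pregnancy tests are to be conducted in women of childbearing potential within 72 hours of C1D1". The Appendix A row has marks at baseline and Cycle 1 Day 1 and nowhere else.

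**The checks before SIR-Spheres in Cohort 1.** Section 7.3.4 (Cycle 1 Day 22) lists the assessments due within 7 days before SIR-Spheres. Footnote q names them: "The Cycle 1 Day 22 physical examination, ECOG performance status, CBC, CMP, and PT/PTT/INR, tumor marker (CEA), adverse event evaluation, and concomitant medication review". A pregnancy test is in neither list. Section 7.3.5 then sets the condition for treatment, judged against Section 3.1: "SIR-Spheres may not be administered until the patient's hematologic, liver and renal function assessments performed per Section 7.3.4 have been re-confirmed as eligible".

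**Other provisions that bear on it.** Exclusion 8 in Section 3.2 reads "Pregnant or lactating". Under inclusion 10, women of childbearing potential, and men with such partners, "are required to use two forms of acceptable contraception, including one barrier method, during their participation in the study". Section 3.3 lists pregnancy as a reason to stop study treatment. Section 8.1 says "SIR-Spheres microspheres are to be administered in accordance with the terms of its marketing authorization and in accordance with institutional standard of practice", and Section 8.1.2 repeats the reference to the marketing authorization.

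**Cohort 2.** SIR-Spheres is itself the Cycle 1 Day 1 treatment (Section 7.4.2), so the 72-hour test in Section 7.4.1 comes just before the implant.

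**The concern.** The test is tied to Cycle 1 Day 1, but that day is a different treatment in each cohort. In Cohort 2 it is the 90Y implant. In Cohort 1 it is the first regorafenib dose, and the implant comes four weeks later. The protocol asks for fresh blood counts, chemistry, examination and tumor marker before the Cohort 1 implant, yet carries pregnancy status forward from entry.

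At stake is the safety of women of childbearing potential in Cohort 1. Section 1.1 describes microspheres that lodge in the vessels feeding the tumor and emit radiation. A daily tablet can be stopped when a pregnancy is found; an implant cannot be taken back. Discontinuation under Section 3.3 protects the patient only if the pregnancy is known beforehand, and no test scheduled after Cycle 1 Day 1 would reveal it.

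**Working it through.** The plan gives no figure for the age of the test, so it has to be worked out from the calendar.

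**Inputs**

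| Input | Value | Source |
|---|---|---|
| Pregnancy test | 0 to 3 days before Cycle 1 Day 1 | Protocol 7.3.1, 7.3.2, 7.4.1 |
| Regorafenib before SIR-Spheres, Cohort 1 | 21 days, then a 7-day hold | Protocol 1.2, 5.1 |
| Mapping (angiogram and MAA scan) | 7 to 4 days before SIR-Spheres, in week 4 | Protocol 7.2 |
| Limit on other pre-implant checks | 7 days | Protocol 7.3.4, Appendix A footnote q |
| SIR-Spheres day, Cohort 2 | Cycle 1 Day 1 | Protocol 7.4.2 |

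**Formula.** Age of test at implant = (implant day − 1) + t, where t is 0 to 3 days.

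**Cohort 1.** Implant day = 1 + 21 + 7 = Day 29. Age = 28 + 0 to 28 + 3 = **28 to 31 days**. Each day of delay adds one day.

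**Cohort 2.** Implant day = 1. Age = 0 + 0 to 0 + 3 = **0 to 3 days**.

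**At mapping in Cohort 1.** Mapping falls on Day 29 − 7 = 22 to Day 29 − 4 = 25, which agrees with week 4. The listed test is then 21 + 0 to 24 + 3 = 21 to 27 days old.

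**Sensitivity to the reading of the text**

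- The Figure 1 table, whose columns may not have survived conversion from PDF, shows SIR-Spheres under week 6. Sections 1.2 and 7.2 and the 28-day cycle support Day 29. If week 6 were meant (Days 36 to 42), the test would be 35 to 38 days old on the first day of that week and 41 to 44 on the last.
- Section 7.1 and footnote i could be read to allow a test up to 3 days after Cycle 1 Day 1. The minimum age would then be 29 − 4 = 25 days. Sections 7.3.1 and 7.3.2 exclude that reading.

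**Does another rule close the gap?**

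- The 7.3.5 condition covers three organ functions and points to Section 3.1. The pregnancy exclusion is in Section 3.2, which governs study entry, so the condition does not reach it.
- Footnote q names eight items. One of them, PT/PTT/INR, applies at Day 22 only to patients on Coumadin (Section 7.3.4), which leaves seven for every patient. None is a pregnancy test.

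**Effect of a Day 22 test done before mapping.** Taken on Days 22 to 25, it would be 29 − 25 = 4 to 29 − 22 = 7 days old at the implant. That is 28 − 7 = 21 to 31 − 4 = 27 days fresher than the listed test.

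**The case against.** The strongest reply is that the rule is the same in both cohorts: one test before treatment starts, then contraception, discontinuation if pregnancy occurs, and pregnancy reporting (Section 11.3.8, Appendix E). The age difference at implant follows from the sequence under study. Cohort 2 likewise has no repeat test before its first regorafenib dose, 2 to 4 weeks after SIR-Spheres. This stands in part. A reader might infer that the protocol contradicts itself or sets a looser rule for Cohort 1, and the documents support neither. What remains is that one rule gives very different assurance before the one step that cannot be undone.

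The second reply is that labelling or institutional practice, which Section 8.1 makes binding, may already require a test before the implant. This also stands as a limit. A reader might infer that Cohort 1 women would reach the implant untested. The documents do not show that, because the package insert and site procedures are not part of them. They show only that the protocol schedules no test, although it spells out the organ-function checks and, for Cohort 2, a 72-hour pregnancy test before the same implant.

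The third reply is that the risk is very small. Agreed. The patient has an entry test, must use contraception, and has an examination, adverse event evaluation and medication review within 7 days before SIR-Spheres. None of these is a pregnancy test, but together they make an undetected pregnancy unlikely.

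**Conclusion.** The point holds for Cohort 1 as a low-probability safety gap with a cheap remedy. At a Day 29 implant the only listed pregnancy test is 28 to 31 days old. That compares with a 7-day limit on the other pre-implant checks and with 0 to 3 days at the same implant in Cohort 2.

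The figure assumes Cycle 2 Day 1 falls on schedule and the test is done before the first dose, as Sections 7.3.1 and 7.3.2 say. Delay makes the test older. Confidence is high about what the schedule lists, and limited about what sites would do under labelling and local practice.

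The documents do not give the number of women of childbearing potential or a conception rate on the required contraception, so the number of pregnancies at risk is not estimated. A reader might also infer that the trial's results are compromised. Nothing supports that: no effect on ORR, PFS or OS is claimed, and none on the primary safety analysis has been shown.

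**What to change.** For women of childbearing potential in Cohort 1:

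1. Add a serum or urine pregnancy test to Section 7.3.4 and to the Cycle 1 Day 22 column of Appendix A, with footnotes i and q amended to match. Do it before mapping and within 7 days before SIR-Spheres, and repeat it if SIR-Spheres slips past 7 days.
2. In Section 7.3.5, make a negative result a condition for giving SIR-Spheres, alongside the hematologic, liver and renal re-confirmation.

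This brings the test to the footnote q standard (4 to 7 days old at an on-schedule implant), not to the 0 to 3 days of Cohort 2. Matching Cohort 2 would take a test within 72 hours before SIR-Spheres. Mapping is at least 4 days before the implant, so one test cannot be both before mapping and inside 72 hours. The 72-hour test would be an optional addition.

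The cost is about one test per woman of childbearing potential, at a visit where blood is already drawn. That is at most 25 tests even if all 25 Cohort 1 patients were such women, plus any repeats after a delay. A positive or equivocal result could briefly delay mapping or SIR-Spheres while it is confirmed. The wording changes are confined to two sections, two footnotes and one table mark.
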